#### 3.2 Secondary Objectives

- To assess the immunogenicity of IFN beta-1a
- To investigate the efficacy of IV IFN beta-1a on clinical outcomes in hospitalized patients with COVID-19 compared to dexamethasone

### 3.3 Exploratory Objectives

- To investigate the efficacy of IV IFN beta-1a on clinical outcomes in hospitalized patients with COVID-19 compared to dexamethasone
- To measure the pharmacodynamic (PD) effects of IFN beta-1a (MxA and CD73)
- To measure IFN beta levels during the treatment
- To evaluate potential inflammatory markers (PIMs) and interferon signalling markers at protein and RNA level in response to treatment
- To evaluate genetic susceptibility to IFN beta-1a treatment
- To investigate study treatment discontinuation rate of IFN beta-1a compared to dexamethasone
- To investigate the effect of IMPs on viral burden (quantitative) in blood during the disease course
- To investigate the efficacy of study treatment based on SARS-CoV-2 variant
- To investigate the efficacy of study treatment based on the vaccination status

### 3.4 Outcome Measures

#### 3.4.1 Primary outcome measure

- Clinical status at Day 14 (where first day of study drug is Day 1) as measured by WHO 9-point ordinal scale:
  0. No detectable infection;
  1. Not hospitalized, no limitations on activities;
  2. Not hospitalized, limitation on activities;
  3. Hospitalized, not requiring supplemental oxygen;
  4. Hospitalized, requiring supplemental oxygen;
  5. Hospitalized, on non-invasive ventilation or high flow oxygen devices;
  6. Hospitalized, on invasive mechanical ventilation;
  7. Hospitalized, on mechanical ventilation plus organ support: RRT or ECMO;
  8. Death.

#### 3.4.2 Secondary outcome measures

- Clinical status at Day 28 as measured by WHO 9-point ordinal scale:
  0. No detectable infection;
  1. Not hospitalized, no limitations on activities;
  2. Not hospitalized, limitation on activities;
  3. Hospitalized, not requiring supplemental oxygen;
  4. Hospitalized, requiring supplemental oxygen;

5. Hospitalized, on non-invasive ventilation or high flow oxygen devices;
6. Hospitalized, on invasive mechanical ventilation;
7. Hospitalized, on mechanical ventilation plus organ support: RRT or ECMO;
8. Death.

- Outcome measures relating to the efficacy of IFN beta-1a treatment:
  - In-hospital mortality at Day 28 and Day 90
  - Overall (all-cause) mortality at Day 28 and Day 90

### 3.4.3 Exploratory outcome measures

- Incidence of ARDS
- Incidence of Acute Kidney Injury (AKI)
- Incidence of new mechanical ventilation
- Days alive and free of renal support at Day 28
- Days alive and free of ECMO at Day 28
- Days alive and free of oxygen support, Day 28
- ICU-days at Day 28
- Days on mechanical ventilation on Day 28
- Length of Hospital stay among survivors at Day 90
- Incidence of study treatment discontinuation and transition to an open label corticosteroid
- PD markers (CD73 and MxA) possibly related to the natural IFN responses, as well as to the IFN beta-1a treatment
- Potential inflammatory and interferon signalling (e.g., IL-6, IL-8) markers at a protein and RNA level (Nanostring) in response to treatment.
- Quantitative analysis (PCR) for SARS-CoV-2 from serum samples.
- Genetic susceptibility to IFN beta-1a treatment, including but not limited to, by screening for SNP rs9984273 and surrounding area which is the glucocorticoid regulatory motif area of IFN alpha/beta receptor subunit 2 (IFNAR2)
- Association of the efficacy outcome measures of study treatment with the variant of SARS-CoV-2
- Association of the efficacy outcome measures of study treatment with the vaccination status

## 4 OVERALL DESIGN AND PLAN OF THE STUDY

### 4.1 Overview

This is a multicentre Phase II, double-blind, randomized and controlled, study of the safety and preliminary efficacy of IV IFN beta-1a compared with dexamethasone in adult patients diagnosed with COVID-19 needing hospitalization, but not invasive mechanical ventilation or high flow/presurized supplemental oxygen. The primary endpoint safety and tolerability of IV IFN beta-

1a, and primary efficacy endpoint is WHO ordinal scale for clinical improvement (WHO OSCI) score at D14. Both treatment groups will receive standard care according to current treatment guidelines, except open-label corticosteroids during study days D1-D6 (or other co-medication with potential of interacting with IFN beta-1a; [Section 5.7](#)). If the patient receives (oral or intravenous) glucocorticoids during study days D1-D6, the IMP will be discontinued, and the patient will continue with in all follow-up study assessments.

[figure not shown]
Approximately 140 subjects are planned. Patients with COVID-19 admitted to hospital will undergo screening during which written informed consent will be obtained and eligibility assessed. Not more than 48 hours may elapse between arrival to hospital and administration of the first dose of study drug. An interactive web-response system (IWRS) will be used to randomise the patients using age and gender as stratification parameters.

Following randomization, patients will be treated daily with IFN beta-1a 10 µg or dexamethasone 6 mg as an IV bolus for 6 days and will undergo daily assessments while hospitalized. The main analysis and reporting will use D14 and D28 data. D90 data will be analysed separately. Final follow-up will occur at D90 by phone or through medical records. The overall duration of the study for a patient is therefore 3 months. During the long-term follow-up periods patient care will follow normal hospital procedures, as appropriate. The study will be completed when the last patient completes D90 study assessment. The study design is summarised in [Figure 1](#).

Discontinuation criteria for individual patients and the entire study are described in [Section 4.8.1](#).

The study design incorporates an Independent Data Monitoring Committee (IDMC) that will review ongoing safety (i.e., adverse events [AEs] and serious AEs [SAEs]) and will also make recommendations to the Sponsor as described in the IDMC charter. Details of the IDMC are given in [Section 8.8](#).

A schedule for the tests and assessments to be conducted during this study is given in [Section 6 \(Table 2\)](#).

**Figure 1. Study Design**

a Not more than 48 hours may elapse between arrival to hospital and administration of the first dose of study drug on D1. Once eligibility has been met, randomization can occur during screening or pre-dose on D1.

b Assessments are described in the Schedule of Procedures in [Table 2](#).

c Telephone contact or searched from medical records if the patient cannot be contacted.

Abbreviations: D=day; FU=follow-up

## 4.2 Criteria for Evaluation of the Safety and Efficacy

### 4.2.1 Criteria for Evaluation of Safety

- AEs up to D28, AEs occurring after D28 if the investigator considers there is a causal relationship with the study drug and all deaths up to D90.
- Physical examination to the extent available, vital signs and available laboratory results (biochemistry and haematology including pre-dose D1, D2-D7, D10, D14, D28/last day in hospital laboratory tests ([Table 2](#))) while hospitalized.
- Immunogenicity as measured by anti-drug antibodies (ADA)

### 4.2.2 Criteria for Evaluation of Efficacy

#### Primary Efficacy Endpoint:

- Clinical status at D14 as measured by WHO 9-point ordinal scale:
  - 0 - No detectable infection;
  - 1 - Not hospitalized, no limitations on activities;
  - 2 - Not hospitalized, limitation on activities;
  - 3 - Hospitalized, not requiring supplemental oxygen;
  - 4 - Hospitalized, requiring supplemental oxygen;
  - 5 - Hospitalized, on non-invasive ventilation or high flow oxygen devices;
  - 6 - Hospitalized, on invasive mechanical ventilation;
  - 7 - Hospitalized, on mechanical ventilation plus additional organ support: renal replacement therapy, ECMO
  - 8 - Death

#### Secondary Efficacy Endpoints:

- Clinical status at D28 as measured by WHO 9-point ordinal scale (above)
- Secondary endpoints relating to the efficacy of IV IFN beta-1a treatment:
  - In-hospital mortality at Day 28 and Day 90
  - Overall (all-cause) mortality at Day 28 and Day 90

### 4.2.3 Criteria for Evaluation of Exploratory Endpoints

#### Exploratory Efficacy Endpoints:

- Exploratory endpoints relating to the efficacy of IV IFN beta-1a treatment in comparison to dexamethasone:
  - Incidence of ARDS
  - Incidence of AKI
  - Incidence of new mechanical ventilation
  - Days alive and free of renal support at Day 28
  - Days alive and free of ECMO at Day 28
  - Days alive and free of oxygen support at Day 28
  - ICU-days at Day 28
  - Days on mechanical ventilation on Day 28
  - Length of Hospital stay among survivors at Day 90

- Incidence of study treatment discontinuation and transition to an open label corticosteroid
- Association of efficacy outcome measures of study treatment with the vaccination status

### Exploratory Laboratory Endpoints:

- Change in the treatment-specific exploratory biomarkers (MxA and CD 73) and PIMs (pre-dose on D1, D3, D5 and D7 for hospitalized patients) and Interferon beta (pre-dose on D1, D1 (5 minutes after study drug dosing), D3 and D7).
- Viral clearance for SARS-CoV-2 infection by D14 (viral RNA copy number pre-dose D1 and D4, D7, D10 and D14 (if subject's discharge is before D14, the specimen is obtained also on the day of discharge))
- A blood sample will be taken for pharmacogenetic analysis of the genetic susceptibility in responding to IFN beta-1a treatment. Under specific examination is SNP rs9984273 and surrounding area which is the glucocorticoid regulatory motif area of IFN alpha/beta receptor subunit 2 (IFNAR2). According to the previous Phase III Study (FPCLI002) this polymorphic site may determine responsiveness to IFN beta-1a treatment and outcome. The sub-groups carrying polymorphism in this region will be analysed separately for the Study outcome measures.
- Association of efficacy outcome measures of study treatment with the variant of SARS-CoV-2

### 4.3 Justification of the Study Design

This is a Phase II study to evaluate the safety and efficacy of IFN beta-1a in comparison to dexamethasone in the treatment of subjects with COVID-19. The study is designed as a double-blind, randomized, parallel-group, controlled, multicentre clinical study.

At present there is no approved pharmacological treatment for the prevention of ARDS. The only currently available treatment for mechanically ventilated COVID-19 patients is dexamethasone, but still COVID-19 mortality to ARDS remains high. Because of the lack of an effective pharmacological agent, glucocorticoids are widely used because of their anti-inflammatory properties. However, they may dampen natural anti-viral response of IFN beta signalling. Further, overlapping use of glucocorticoids may block IFN beta-1a from up-regulating CD73 on the lung endothelium. Therefore, the current approach is to investigate the use of IFN beta-1a before corticosteroids (or other medications with immunosuppressive activity) are indicated for COVID-19 and to prevent disease aggravation to ARDS.

The study target population is defined to subjects requiring oxygen supplementation (< 8 l/min) in order to comply with the treatment guidelines (<https://www.covid19treatmentguidelines.nih.gov/therapeutic-management/>). The IFN beta-1a treatment arm is not to receive dexamethasone for study days D1-D6. This is justified with the anticipated anti-viral effects of IFN beta and clinical observations of severity of the disease associated with a deficiency in IFN signalling, and uncertainty of the benefit from dexamethasone in mild COVID-19 (see [Section 2.6](#) for detailed justification for the study setting). However, should the study subjects condition worsen during the early course of the study, while the IMP is being administered (Study days D1-D6), the IMP can be discontinued and dexamethasone initiated according to the discretion of the attending physician, ideally after a discussion with the local study investigator, if the clinical condition of the patient permits it.

#### 4.4 Study Population

The study population will consist of hospitalized patients due to confirmed SARS-CoV2 infection during the previous 7 days. Study subjects must meet all the inclusion criteria and none of the exclusion criteria to be enrolled in the study. The inclusion and exclusion criteria apply during screening and prior to administration of the first dose of study drug on D1.

#### 4.5 Inclusion Criteria

*The inclusion and exclusion criteria apply during screening and prior to administration of the first dose of study drug on study Day 1.*

1. Age  $\geq$ 18 years
2. Positive SARS-CoV-2 test by PCR or other diagnostic method within the past 7 days
3. Admission to hospital with respiratory symptoms of COVID-19 requiring hospital care and oxygen supplementation ( $\leq$  8L/min)
4. Respiratory symptom onset no more than 7 days prior to hospital admission
5. Informed consent from the subject or the subject's personal legal representative or a professional legal representative must be available

#### 4.6 Exclusion Criteria

1. Unable to screen, randomize and administer study drug within 48 hours from arrival to hospital
2. Systemic corticosteroid, baricitinib or tofacitinib (or other JAK-STAT signalling pathway inhibitors) therapy within 7 days prior to arrival to hospital or planned for the next days
3. Known hypersensitivity or contraindication to natural or recombinant IFN-beta-1a or its excipients, or to dexamethasone or its excipients
4. Currently receiving IFN-beta-1a therapy
5. Home assisted ventilation (via tracheotomy or non-invasive) except for Continuous positive airway pressure (CPAP) / Bilevel Positive Airway Pressure (BIPAP) used only for sleep-disordered breathing
6. Participation in another concurrent interventional pharmacotherapy trial during the study period
7. Decision to withhold life-sustaining treatment; patient not committed to full support (except DNR after cardiac arrest only)
8. Woman known to be pregnant, lactating or with a positive pregnancy test (urine or serum test)
9. Subject is not expected to survive for 24 hours
10. Subject has liver failure (Child–Pugh grade C)
11. Any clinical condition that in the opinion of the attending clinician or Investigator would present a risk for the patient to participate in the study

#### 4.7 Confirmation of Patient Eligibility

To ensure appropriate enrolment into the study there will be a formal confirmation of eligibility process utilising the following procedure:

An electronic Case Report Form (e-CRF) with mandatory fields for completion and a checklist of inclusion and exclusion criteria; all items will need to be completed. The IWRS System will prompt the Investigator to confirm eligibility before allowing a patient to progress to randomization.

With this method, only those patients whose data are recorded as meeting eligibility criteria can be randomized.

## 4.8 Patient Withdrawal and Replacement

### 4.8.1 Discontinuation Criteria

Subject may withdraw from the entire study, including follow-up, at any time without penalty and for any reason without prejudice to their future medical care; they are not obliged to state their reasons for withdrawing. The decision to withdraw can be made by the subject or their Personal Legal Representative (PerLR) or Professional Legal Representative (PrfLR).

Subjects may be **withdrawn from the study** under the following circumstances:

- Protocol violations including non-compliance with study procedures or subject lost to follow-up
- Subject, PerLR or PrfLR request

The Investigator must ensure that the status page in the e-CRF for the **end of the study** is completed. Necessity for concomitant glucocorticoid treatment during study days D1-D6 may occur (for treating conditions listed in the [Table 1](#) or based on Investigator's judgement for other conditions necessitating **systemic (oral or intravenous)** glucocorticoid treatment) or deterioration of the study subjects condition due to COVID-19 may lead to IMP discontinuation and initiation of open label corticosteroids for COVID-19, neither of these are a condition for withdrawal.

Subject may be required to **withdraw from study drug** after discussion with the Sponsor and/or Investigator for the following reasons:

- Safety issues
- At the discretion of the attending physician if it is considered to be in the subject's best interest

Subjects who discontinue study drug should continue in the study for follow-up to D90. The Investigator must ensure that the status page in the e-CRF is completed and every effort should be made to minimize missing data.

In all cases, the reason(s) for withdrawal, including the primary reason, must be recorded in the e-CRF. If a subject is prematurely withdrawn from the study drug for any reason, the Investigator must make every effort to perform the evaluations described for the follow-up visits. Any on-going AEs should be followed up to resolution or D28 whichever is the sooner. D90 assessment for mortality should be sought to the extent possible. See also [Sections 8.6.2](#) and [8.6.3](#).

If a subject (or their representative) withdraws consent and still agrees to undergo a final examination, this will be documented in the e-CRF and the Investigator's copy of the Informed Consent Document (ICD), which will be countersigned and dated by the subject (or PerLR or PrfLR).

Subjects who have discontinued or withdrawn their consent will not be replaced. Data and biospecimen collected before withdrawal will be used.

The study will be terminated if, in the opinion of the Sponsor, significant safety concerns arise during the conduct of the study.

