### 7.1.2 Protocol Deviations

Deviations from the protocol including violations of inclusion/exclusion criteria will be classified as “minor” or “major” in conjunction with the Sponsor and Medical Monitor. Relevant major deviations from the protocol will lead to the exclusion of that patient from the PPS. Deviations will be defined prior to unblinding.

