## 7.2 General Considerations

All statistical tests will be two sided and will be performed at the significance level of 0.05, unless otherwise stated.

Continuous data will be summarised by treatment group using descriptive statistics (number, mean, median, standard deviation [SD], minimum and maximum). Categorical data will be summarised by treatment group using frequency tables (frequencies and percentages).

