#### 7.2.1.4 Missing Data Handling

In general, data will not be imputed for the primary efficacy analysis or the safety analysis. For other efficacy analyses, where relevant, imputations will use the last observation carried forward method for patients in the analysis. Additional details will be given in the SAP.

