#### 7.2.1.5 Intercurrent events

Use of open label corticosteroids (i.e., discontinuation of study IMP during D1-D6 and initiation of corticosteroids due to deterioration of the study subjects' condition, or initiation of corticosteroids D7 onwards) is an intercurrent event anticipated to affect the study outcomes. The primary analysis is planned to follow the treatment policy strategy (using FAS dataset). As sensitivity analyses, also other strategies under the estimands framework (ICH E9 (R1) addendum) will be applied to account

for this intercurrent event. Details of these analyses will be described in SAP. The frequency and magnitude of the effect of the use of corticosteroids to the study outcomes will be also evaluated during the planned Interim Analysis.

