### 7.4 Determination of Sample Size

140 patients will be randomised 1:1 for active: comparator. Conditional Power re-assessment will be conducted at interim analysis after circa 70 patients have been enrolled and followed up for the primary efficacy endpoint variable. The primary variable is the clinical status at Day 14 using the WHO 9-point scale (0=no detectable infection to 8=death). It will be analysed using ordinal logistic regression model comparing the odds of having better clinical status (smaller number in the 9-point scale) at Day 14 between treatment groups. The sample size is based on an assumption of odds ratio of 0.43 between groups leading to a power of 80% with 70 evaluable patients per group. In the interim analysis the conditional power will be calculated based on the observed result and the sample size will be increased in case the conditional power is in the predefined promising zone. The details of interim analyses will be given in IDMC charter created at the study initiation and in an interim analysis plan which will be finalised before breaking the blind for interim analysis.

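### Protocol 4.8.1 lets the study withdraw a dosed patient from all follow-up for a protocol violation, which can leave an FAS member without a Day 14 score

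*Protocol*

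**What the plan says.** **Withdrawal.** Protocol 4.8.1 has two separate lists. The list for withdrawal from the study contains "Protocol violations including non-compliance with study procedures or subject lost to follow-up" and a request by the subject or a legal representative. The list for withdrawal from study drug contains safety issues and the attending physician's discretion. For patients in the second group the section says: "Subjects who discontinue study drug should continue in the study for follow-up to D90". It also states that glucocorticoid need on D1-D6, or deterioration leading to open-label corticosteroids, is not a condition for withdrawal, and it asks sites to keep missing data to a minimum.

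**After withdrawal from the study.** Section 6.5 requires the procedures for the last day of involvement and follow-up of ongoing AEs to resolution or Day 28. Section 4.8.1 asks for D90 mortality where possible. Neither requires a Day 14 status.

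**Violations.** Section 7.1.2 classifies "Deviations from the protocol including violations of inclusion/exclusion criteria" as minor or major; relevant major ones lead to exclusion from the PPS. Under 4.8.2 ineligibility makes a patient a screen failure only before the first dose, and dosed patients are not replaced.

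**Analysis.** Section 7.1.3 puts every randomised and dosed patient in the FAS, as randomised, and bases the primary analysis on it. Section 7.2.1.4: "In general, data will not be imputed for the primary efficacy analysis or the safety analysis". Section 7.2.1.5, on open-label corticosteroid use: "The primary analysis is planned to follow the treatment policy strategy (using FAS dataset").

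**SAP.** Sections 2 and 6 record termination with five dosed patients and plan listings and descriptive tables only.

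**The concern.** Whether a patient broke a protocol rule and whether that patient's outcome is collected should be separate matters. The analysis sections keep them separate: a violator counts in the FAS and drops out only of the PPS. Section 4.8.1 joins them again, because a violation can end participation altogether.

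If that happens before Day 14 and the patient is alive, the ordinal score is missing, nothing in general replaces it, and the ordinal model omits the patient. The FAS analysis then moves towards the PPS analysis that is meant to test it. Part of the AE record to Day 28, which serves the co-primary safety objective, may also be lost. Withdrawal of this kind is avoidable, because the study and not the patient initiates it. No criteria guide its use, so sites may differ.

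**Working it through.** **1. The path through the text.**

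| Step | Protocol section | Rule |
|---|---|---|
| Ineligibility or another violation is found after the first dose | 4.8.2, 7.1.2 | No longer a screen failure; it is a deviation |
| Site's option | 4.8.1 | May withdraw from the study |
| Data then required | 6.5 | Last-day procedures and ongoing AEs; no Day 14 contact |
| Replacement | 4.8.2 | None after dosing |
| Missing Day 14 score | 7.2.1.4 | In general not imputed |
| Analysis set | 7.1.3 | Still in the FAS; a major violator leaves only the PPS |

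Followed in order, these rules produce an FAS member without a primary outcome.

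**2. How the protocol treats comparable departures.** Section 5.3 stops study drug after a dose delay of more than 12 hours but keeps collecting all data. Section 5.4 keeps collecting data after unblinding. Section 4.8.1 protects patients who go on to open-label corticosteroids. The synopsis (Design) extends the corticosteroid handling, which is to stop the IMP and continue assessments, to JAK-STAT inhibitors; 4.8.1 does not repeat that extension. Stopping drug while keeping data is the usual rule in this protocol, and the violation ground departs from it.

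**3. The plan's own power figure.** Inputs: "All statistical tests will be two sided and will be performed at the significance level of 0.05, unless otherwise stated" (7.2); "The sample size is based on an assumption of odds ratio of 0.43 between groups" and "leading to a power of 80% with 70 evaluable patients per group" (7.4). The planned total of 140 equals the evaluable number, so there is no allowance for loss.

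Whitehead's proportional-odds formula for 1:1 allocation is N = 12(z₀.₉₇₅ + z₀.₈₀)² / [(ln OR)²(1 − S)], where S is the sum of the cubed mean category probabilities.

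- (1.960 + 0.842)² = 7.849 and (ln 0.43)² = 0.7123.
- 12 × 7.849 / 0.7123 = 132.2, so N = 132.2 / (1 − S).

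The documents do not give the Day 14 distribution, so S is an assumption.

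| S | N for 80% power | Power with 140 |
|---|---|---|
| 0.012 (nine equal categories) | 134 | 81.7% |
| 0.0555 | 140 | 80.0% |
| 0.10 | 147 | 78.1% |
| 0.20 | 165 | 73.2% |

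The stated 80% cannot be reproduced uniquely, but it is compatible with S of about 0.055. Nothing here shows it to be wrong.

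**4. Power if Day 14 scores are lost.** Take the stated 80% as correct. The standard error of the log odds ratio is 0.844 / 2.802 = 0.301. With k scores lost it becomes 0.301 × √(140/(140 − k)), and power is Φ(2.802 × √((140 − k)/140) − 1.960).

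- k = 7 (5%): 2.802 × 0.9747 − 1.960 = 0.771, power 78.0%.
- k = 14 (10%): 2.802 × 0.9487 − 1.960 = 0.698, power 75.7%.

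The loss rates are assumed.

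**5. Bias.** Its sign depends on who is withdrawn, which the documents cannot tell us. Assume two identical arms of 70 with counts 28/18/4/7/4/4/1/4 in categories 1 to 8, and remove patients from one arm only. Removing three patients with scores 4, 5 and 6 moves the fitted odds ratio from 1.00 to 0.91. Removing five with scores 4 to 6 moves it to 0.85. Removing three with scores 1, 2 and 4 leaves it at 1.00. With a standard error of about 0.31, even the five-patient shift (|ln 0.85| = 0.16) is about half a standard error. These are constructed cases, not estimates.

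**The case against.** **A stronger reading that does not hold.** A reader might infer that the withdrawal ground contradicts the treatment-policy strategy. It does not. Section 7.2.1.5 defines that strategy for one intercurrent event, open-label corticosteroid use, and 4.8.1 says this event is not a condition for withdrawal. The two sections agree. The tension is with the FAS principle and with the completeness of Day 14 data.

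**Informative loss through rescue medication.** A reader might also infer that patients given prohibited rescue treatment would be lost. Corticosteroid users are protected in 4.8.1, and the synopsis covers JAK-STAT inhibitors by the same principle. What remains is that 4.8.1 should be aligned with the synopsis.

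**Loss is not automatic.** Withdrawal is discretionary and may come after Day 14. No section says that a patient found ineligible after dosing should be withdrawn; that follows only from reading 4.8.1 together with 7.1.2. Section 4.7 checks eligibility before randomisation. Section 4.8.1 also asks for the follow-up evaluations when a patient is taken off study drug for any reason, so a violator whose drug is stopped is arguably covered. This stands, and it means that 4.8.1 points both ways for the same patient.

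**Other safeguards.** The reason for withdrawal is recorded (4.8.1), disposition is tabulated (7.1.1), and a blinded review decides how missing data and withdrawn patients are handled (section 7). Ongoing AEs and D90 mortality are still pursued, so a death by Day 14 may be captured as category 8. These measures make the loss visible and limit it. They do not supply the Day 14 score of a living patient or new AEs after withdrawal.

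**Size.** The one-arm bias scenario is hypothetical in a double-blind trial. That stands.

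**Conclusion.** The point holds in a limited form. The protocol permits an avoidable, study-initiated loss of the primary outcome in patients whom its own analysis sections keep in the FAS. It does not require that loss.

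The power figures, about 78% at 5% loss and 76% at 10%, rest on two assumptions: that the stated 80% is right, and that losses of that size arise from this ground alone before Day 14. The documents give no violation rate, so the real cost could be close to nothing. The direction and size of any bias are unknown.

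A reader might take this as casting doubt on the trial's reported results. The documents do not support that: with five subjects and a SAP that tests no hypotheses, no ordinal model is planned that could be affected. The defect is one of protocol design. It is a free improvement of minor severity.

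**What to change.** In protocol 4.8.1:

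- Delete protocol violations and non-compliance with study procedures as a ground for withdrawal from the study.
- Keep withdrawal of consent by the subject or legal representative. Keep loss to follow-up, recorded as an outcome and not as a decision to withdraw.
- State that a dosed subject with a violation, including ineligibility found after dosing, continues Day 14, Day 28 and Day 90 follow-up and AE collection, is analysed in the FAS, and is handled through the deviation log and the PPS.
- Align the sentence on open-label corticosteroids with the synopsis, so that continued follow-up after JAK-STAT inhibitor use is stated in both places.

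The cost is a few lines of text. The contacts are already scheduled for every patient in sections 6.1 and 6.4, and neither the sample size nor the analysis model changes. For this terminated trial the change matters only if the protocol is reused as a template.
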